4.2.1 Criteria to Start Next Cycle

- a. Hemoglobin: \geq 8.0 gm/dl (may transfuse PRBCs)
- b. ANC: \geq 750/mm³
- c. Platelet Count: \geq 75,000/mm³ (transfusion independent; \geq 7 days from last transfusion)
- d. SGPT (ALT) \leq 5 x ULN
- e. SGOT (AST) \leq 5 x ULN

4.3. Surgery

Patients may undergo surgical tumor resection at any point during the protocol if it is clinically indicated per treating physician recommendation.

Study drug should be held for at least 72 hours prior to surgery. Patients who undergo resection will require a post-operative MRI of the primary tumor site, preferably within 72 hours after resection. Patients who undergo gross total resection of the target lesion with no measurable disease on post-operative imaging will permanently discontinue study drug. Patients with residual measurable tumor after resection may resume study drug when clinically cleared by medical team (usually 2-4 weeks after resection) and when they meet the criteria described in 4.2.1 to start a new cycle. Measurable tumor for this purpose is defined as tumor with a maximal diameter at least twice the slice thickness of the MRI sequence used to define tumor dimensions. Postoperative MRI will be used as the new baseline for subsequent response determinations.

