3.1. Inclusion Criteria

- 1) Age: Patients must be less than 22 years at the time of enrollment; there is no lower age limit.
- 2) All participants must have an identified pathogenetic constitutional *NF1* mutation OR the clinical diagnosis of NF1 using the NIH Consensus Conference criteria (**See Appendix 1**).

- 3) Diagnosis: LGG (WHO Grade 1 and 2) of the brain and spinal cord are eligible. Histologic confirmation of tumor is not necessary in the presence of consistent clinical and radiographic findings. Biopsy for histologic diagnosis is required if there is clinical suspicion for a high-grade tumor; special attention is recommended in older adolescents or young adults to the potential for malignant transformation. Patients with metastatic disease are eligible.
- 4) Patients must meet at least one of the following criteria for progression or recurrence of a previously treated target tumor:
 - a. Progression or recurrence on MRI.
 - b. New or worsening neurologic symptoms attributable to the target tumor.
 - c. For patients with OPG: visual worsening, defined as worsening of visual acuity (VA) or visual fields (VF) documented within the past year by examination or history, attributable to tumor.
- 5) Measurable Disease: Patients must have two-dimensional measurable tumor $>1\text{cm}^2$.
- 6) Prior Therapy: Patients must have had at least one prior medical treatment for the target LGG.
- 7) Performance Level: Patients must have a performance status of equal or $>$ than 50 using Karnofsky for patients equal or \geq 16 years of age and Lansky for patients $<$ 16 years of age. **See Appendix 2 for scale.**
- 8) Patients must have recovered to grade ≤ 1 from any acute toxicities from all prior treatments. to enroll on this study and meet time restrictions from end of prior therapy as defined below:
 - a. Myelosuppressive chemotherapy: must have received the last dose of myelosuppressive therapy at least 4 weeks prior to study registration, or at least 6 weeks if nitrosourea.
 - b. Investigational/biological agent: Patient must have received the last dose of other investigational, immunotherapy, or biological agent $>$ 14 days prior to study registration or at least 5 half-lives, whichever is greater. Bevacizumab last dose $>$ 36 days prior to enrollment.
 - c. Radiation therapy: Patients SHOULD NOT have received prior irradiation.
 - d. Study specific limitations on prior therapy: There is no limit on the number of prior treatment regimens.

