14. STATISTICAL CONSIDERATIONS

Primary Endpoints

The primary endpoint of the study is objective response rate (defined as CR or PR) during the first 12 months of treatment. Response will be assessed through the time of the post-12th cycle tumor assessment, or through the last tumor assessment time during this nominal period for patients in follow-up but who have withdrawn from protocol therapy, or through the last available tumor assessment for patients who are lost to follow-up during this time.

The percent change in tumor sizes compared to baseline will be recorded at each evaluation time and will be used to define the categorical response as described below, per the definition of CR, PR, MR, SD, and PD in section 10.4.

- For tumors that regress compared to baseline during the assessment period without first satisfying the criteria for progressive disease (PD), response will be defined at the nadir of the tumor size compared to baseline provided that the percent reduction at the nadir satisfies the definition of CR, PR, or MR per section 10, with the response value of CR, PR, or MR determined by the percent reduction at this time.

The associated time of response will also be recorded.

- For tumors that progress compared to baseline and satisfy the definition of PD without first satisfying the criterion at least for minor response (MR), response will be defined at the first time at which the percent increase in tumor size compared to baseline satisfies the criterion for PD. The response value will be PD. The associated time of response will also be recorded. Progressive disease could be confirmed with a short follow-up MRI (+/- 6 weeks) per treating physician decision, otherwise continue with MRI interval per protocol.
- For tumors that neither regress sufficiently to satisfy the criterion for MR nor progress sufficiently to satisfy the criterion for PD during the assessment period, the response value will be determined to be SD.

Patients will be considered evaluable for response if they have received at least one dose of treatment and have at least one post-baseline tumor assessment.

Patients who undergo gross total resection while on study will be excluded from further response at the time of surgery. Patients who have measurable residual disease (at least twice the thickness of the MRI slide) after resection will be able to continue study drug and the post-op MRI will be used as the new baseline.

Secondary Endpoints

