- Progression free survival (PFS), defined as the time from start of treatment to the first occurrence of tumor recurrence, tumor progression, occurrence of a second malignancy, or death from any cause. Patients event-free at last follow-up will be censored in analysis. PFS will be determined at 12, 24 and 60 months.
- Objective response rate (defined as CR or PR) after 24 cycles of treatment. Response will be assessed through the time of the post-24th cycle tumor assessment, or through the last tumor assessment time during this nominal period for patients in follow-up, but who have withdrawn from protocol therapy, or through the last available tumor assessment for patients who are lost to follow-up during this time.
- Clinical benefit defined as (CR+PR+MR+SD). Clinical benefit will be assessed through the time of the post-12 and 24th cycle tumor assessment, or through the last tumor assessment time during this nominal period for patients in follow-up but who have withdrawn from protocol therapy, or through the last available tumor assessment for patients who are lost to follow-up during this time.
- The grade and duration of CTCAE toxicities observed during treatment using CTAE version 5.0.
- Evaluation for visual acuity for patients with optic pathways gliomas will be assessed at 12 months and 24 months from starting therapy. Patient visual outcome will be assessed through the time of the post-12th and 24th cycle visual assessment, or through the last visual assessment time during this nominal period for patients in follow-up but who have withdrawn from protocol therapy, or through the last available tumor assessment for patients who are lost to follow-up during this time.

Exploratory Endpoint

The RANO criteria for response assessment will be determined and descriptively compared to the primary response using RAPNO.

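### After partial resection the post-operative MRI becomes the new response baseline and the participant stays in the primary count, so post-operative change unrelated to the drug can be scored as CR or PR

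*Combined protocol and SAP*

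**What the plan says.** Section 4.3 permits surgery throughout: "Patients may undergo surgical tumor resection at any point during the protocol if it is clinically indicated per treating physician recommendation". A post-operative MRI is required, "preferably within 72 hours after resection". If measurable tumor remains, study drug may resume and the "Postoperative MRI will be used as the new baseline for subsequent response determinations". Measurable here means a maximal diameter of at least twice the slice thickness. At entry, section 3.1 item 5 is stricter: "Patients must have two-dimensional measurable tumor" above 1 cm².

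Section 14 (Primary Endpoints) has the same rule: participants with residual disease "will be able to continue study drug and the post-op MRI will be used as the new baseline". Only complete removal ends response assessment: "Patients who undergo gross total resection while on study will be excluded from further response at the time of surgery". A participant is evaluable if they have "received at least one dose of treatment and have at least one post-baseline tumor assessment", and section 14.3 bases all outcome analyses on evaluable participants. A partly resected participant therefore stays in the primary count.

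Response is taken at the smallest tumor size in the window (section 14). PR is a fall of at least 50% on T2 and T2-FLAIR (section 10.4), cystic components are measured (section 10.2), and no scan to confirm CR or PR is required. PFS events are the "first occurrence of tumor recurrence, tumor progression, occurrence of a second malignancy, or death from any cause"; resection is neither an event nor a censoring point.

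**The concern.** A response should reflect the drug. A scan within days of surgery can show edema, fluid and a cavity as well as residual tumor, and these can settle without treatment. If that scan is the baseline, their settling counts towards the 50% fall, and one scan at the nadir is enough.

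Three features add to this:

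- **Size floor.** The residual may be much smaller than any tumor allowed at entry, so a 50% fall can be a small absolute change.
- **Two baselines.** Section 14 does not say how a status reached against the pre-treatment MRI combines with one reached against the post-operative MRI. Growth before surgery that fell short of PD disappears from the comparison.
- **Secondary endpoints.** Stable residual tumor after surgery counts as clinical benefit, and time gained by surgery counts in PFS.

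The trial is decided by three responders in 16, so one doubtful responder can settle it.

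**Working it through.** **1. The plan's own figure.** Inputs from section 14.2: N = 16, cut-off 3, P0 = 0.05, P1 = 0.25. Exact binomial:

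- Type I error = P(X ≥ 3 | 16, 0.05) = 0.0429 (stated 0.043).
- Power = P(X ≥ 3 | 16, 0.25) = 0.8029, so beta = 0.197 (stated 0.197).

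The design reproduces.

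**2. One re-baselined participant.** Let q be the chance that this participant is scored CR or PR for reasons other than the drug. The documents do not give q, so a range is assumed. The other 15 respond with probability 0.05.

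Type I error = q × P(X ≥ 2 | 15, 0.05) + (1 − q) × P(X ≥ 3 | 15, 0.05) = q × 0.1710 + (1 − q) × 0.0362

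- q = 0.10: 0.0171 + 0.0326 = 0.050
- q = 0.25: 0.0427 + 0.0272 = 0.070
- q = 0.50: 0.0855 + 0.0181 = 0.104
- q = 1 (upper bound): 0.171

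The error passes 0.05 when q exceeds (0.05 − 0.0362) / (0.1710 − 0.0362) = 0.102. At q = 0.05 it stays at 0.043.

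**3. Two re-baselined participants.** Combining Binomial(14, 0.05) with Binomial(2, q) gives 0.057, 0.106 and 0.212 at q = 0.10, 0.25 and 0.50. At q = 1 it is 0.512.

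**4. Size floor.** The floor is twice the slice thickness (section 4.3), with slices from section 10.3. A square residual is assumed, and each diameter is divided by √2 for a 50% fall in area.

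| Sequence | Slice | Smallest diameter | Area | Change per diameter for a 50% fall |
|---|---|---|---|---|
| Axial T2, 1.5 T | 2 mm | 4 mm | 16 mm² | 4 − 2.83 = 1.17 mm |
| Axial FLAIR, both field strengths | 4 mm | 8 mm | 64 mm² | 8 − 5.66 = 2.34 mm |

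Entry requires more than 100 mm². In Table 10 the axial T2 pixel is 200 mm / 256 = 0.78 mm, so 1.17 mm is about 1.5 pixels.

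**5. What the fix does to the design.** Suppose k of the 16 are resected without an earlier response and count as non-responders. At the same cut-off, type I error is P(X ≥ 3 | 16 − k, 0.05) and power is P(X ≥ 3 | 16 − k, 0.25).

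| k | Type I error | Power |
|---|---|---|
| 0 | 0.043 | 0.803 |
| 1 | 0.036 | 0.764 |
| 2 | 0.030 | 0.719 |

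**The case against.** **A reader might infer that the debulking itself is scored as a drug response.** The documents do not support that. Response is the ratio of the current product of diameters to the reference product (section 10.2). Moving the reference to the post-operative scan takes the removed tissue out of that ratio; keeping the pre-treatment baseline after surgery would let it in. What remains is change after the post-operative scan.

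**A reader might also take 0.171 or 0.512 as the expected error.** Those figures need every re-baselined participant to be a certain false responder. The documents give neither the number resected nor that chance. The number is probably small: inclusion criterion 12 selects patients for whom complete resection is not feasible with acceptable morbidity or who refuse surgery, and section 2.1 notes that location can rule surgery out.

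**Existing safeguards.** PR must hold on T2 and FLAIR in a clinically stable or improved patient, and CR also needs disappearance on contrast imaging. PD reached before any minor response fixes the status as PD. All MRIs go to central review. These narrow the problem but do not close it. A patient recovering from surgery can be clinically stable, and section 10.6 gives central review no different baseline rule.

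**The 4 mm floor is the smallest case.** This stands: FLAIR gives 8 mm, PR is read on FLAIR too, and institutional sequences may be substituted. Even 8 × 8 mm is below the entry size.

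**Stopping every endpoint at surgery would do harm.** This also stands for clinical benefit. An early stable disease would be frozen as benefit and later progression discarded, so that endpoint needs a different rule. PFS lies outside the decision rule and its analysis is largely descriptive, so only a sensitivity analysis is warranted there.

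**Conclusion.** The point holds in limited form. The plan re-baselines partly resected participants to an early post-operative scan, keeps them in the three-of-16 count, and does not say how statuses against two baselines combine. It plans no analysis without them. Non-drug post-operative change can therefore be scored as CR or PR.

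The size depends on two unknowns. With one such participant, the type I error is 0.050 to 0.104 for an assumed false-response chance of 10% to 50%, against 0.043 in the plan; 0.171 is the upper bound. If nobody is partly resected in the primary window, nothing changes. The reason to act is that one responder can decide the trial and the repair is only wording.

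**What to change.** In sections 4.3 and 14:

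- **12-cycle and 24-cycle response rates.** Fix response status at the last MRI before any resection of the target lesion, against the pre-treatment baseline. Keep the participant in the denominator, as a non-responder if there is no earlier CR or PR or no on-study MRI before surgery. The evaluability definition needs a clause for that last case. Report responses against a post-operative baseline separately and descriptively.
- **Clinical benefit.** Do not freeze a pre-surgical stable disease as benefit. Continue to count later PD, and report the result with and without resected participants.
- **PFS.** Beside the planned analysis, add a descriptive sensitivity analysis that treats target-lesion resection as an event.

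This extends the cut-off that section 14 already applies to gross total resection. Rules on surgery and continuation of study drug are unchanged, and no new scans are needed. The cost is that a true drug response after partial resection no longer counts toward the three responders: power falls from 0.803 to 0.764 with one resected non-responder and 0.719 with two, while the type I error stays at or below 0.043.

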5. REQUIRED OBSERVATIONS

5.1. Pre-treatment Evaluation

(See Appendix 3)

The following evaluations must be performed within 14 days prior to start treatment unless otherwise indicated. Imaging must be obtained within 4 weeks (28 days) prior to start of treatment. For OPG patients, functional ophthalmology assessment must be performed within 4 weeks (28 days) prior to start treatment.

- A. History (including concomitant medication list), vital signs (RR, HR, BP, temperature and oxygen saturation) and physical examination, including neurologic evaluation.
- B. CBC, differential, platelet count.
- C. CMP: including sodium, potassium, CO₂, chloride, total protein, glucose, AST, ALT, alkaline phosphatase, albumin, calcium, total bilirubin, BUN, creatinine, phosphorous.

- D. Disease evaluation of primary tumor with MRI. MRI must be performed within 4 weeks of starting treatment.
- E. Serum or urine B-HCG in females of childbearing age (**must be repeated if not performed within 7 days of day 1 cycle 1**).
- F. Lansky Play Scale assessment for patients ≤ 16 years of age; Karnofsky score for patients > 16 years old (see Appendix 2).
- G. QOL Assessment after signing consent prior to study drug.
- H. Ophthalmology Functional Assessments (see section 9) only for patients with optic pathway gliomas.
- I. Blood biology studies after signing consent prior to study drug (see section 7).
- J. Study entry form/eligibility checklist to be approved by the study chair or designee prior to starting treatment.

5.2. Evaluation During Treatment (See Appendix 3)

- A. Disease evaluation with MRI brain (with orbital cuts for optic pathway tumors) or spine MRI depending on the primary tumor site every 3 cycles (+/-2 weeks) while on therapy (to be done at the end of the cycle). CSF cytology if clinically indicated. Tumor Evaluation forms are to be completed every 3 cycles while participant is on study. More frequent MRIs can be done at the treating physician discretion. Every MRI performed on participants on study will be submitted to the NFCTC Operations Center for central review at the conclusion of the study.
- B. History, vital signs, physical and neurological examination and concomitant medication list, on cycle 1 day 1 and cycle 1 day 15 (+/-48 hours) and on day 1 (+/-5 days) of each subsequent cycle.
- C. Labs:
 - (a) CBC/differential, platelets are to be obtained on cycle 1 day 1 if not performed within 14 days, on cycle 1 day 8 (+/-48 hours) and cycle 1 day 15 (+/-48 hours) and on day 1 (+/-5 days) of each subsequent cycle.
 - (b) CMP (including sodium, potassium, CO₂, chloride, total protein, glucose, AST, ALT, alkaline phosphatase, albumin, calcium, total bilirubin, BUN, creatinine, phosphorous) are to be obtained on cycle 1 day 1 if not performed within 14 days and on day 1 (+/-5 days) of each subsequent cycle.

Biological correlates SHOULD NOT be obtained on a Friday.

- D. Pregnancy test if female patient is of childbearing age.
- E. Toxicity monitoring and review of medication diary and temperature log at every visit after starting study treatment.
- F. Lansky Play Scale assessment for participants < 16 years of age; Karnofsky score for participants \geq 16 years old at baseline, cycle 1 day 15, and then prior to each cycle (see Appendix 3).
- G. Ophthalmology Functional Assessments (see section 9) only for patients with optic pathway gliomas at the end of cycle 3 (+/- 2 weeks) then every 3 cycles (+/-2 weeks) until end of treatment.
- H. QOL Assessment will be done on day 1 Cycle 6 (+/-2 weeks) and day 1 cycle 12 (+/- 2 weeks) and end of cycle 24 or end of therapy (+/- 2 weeks) (see section 8).
- I. Blood biology studies (see section 7) on day 8 cycle 1, day 15 cycle 1, day 1 cycle 3, 6, and 12, and at the end of treatment. Biology studies should be drawn within 24 hours prior to the next scheduled dose whenever possible. **Mandatory biological correlates SHOULD NOT be obtained on a Friday.** Samples should be at room temperature. Biological blood samples should not be obtained through a fingerstick.

5.3. Evaluation at Completion of Therapy or Relapsed Disease (See Appendix 3)

- A. Disease evaluation: MRI brain (with orbital cuts for optic pathway tumors) with and without contrast or spine MRI with and without with contrast if primary spinal tumor (+/-2 weeks).
- B. History, vital signs, physical and neurological examination, and concomitant medication list (+/- 14 days).
- C. Labs (+/-14 days):
 - (c) CBC/differential, platelets
 - (d) CMP: including sodium, potassium, CO₂, chloride, total protein, glucose, AST, ALT, alkaline phosphatase, albumin, calcium, total bilirubin, BUN, creatinine, phosphorous
- D. Toxicity monitoring and review of medication diary and temperature log
- E. Lansky Play Scale assessment for patients < 16 years of age; Karnofsky score for patients \geq 16 years old (see Appendix 2).
- F. Ophthalmology Functional Assessments (see Section 9) only for patients with optic pathway gliomas (+/-2 weeks).
- G. QOL Assessment (+/-2 weeks) at cycle 24 (+/-2 weeks) (see Section 8).

H. Blood biology studies (see Section 7).

**5.4. Evaluations Off Therapy
(See Appendix 4)**

- A. Disease evaluation: MRI brain (with orbital cuts for optic pathway tumors) with and without contrast or spine MRI with and without contrast if spine is the primary tumor location every 3 months (+/- 4 weeks) for the first 12 months, then every 6 months (+/- 4 weeks) for months 12 - 36, then every 12 months (+/- 6 weeks) until month 60.
- B. Ophthalmology Functional Assessments (see section 8) only for patients with optic pathway gliomas every 3 months (+/- 4 weeks) for the first 12 months, then every 6 months (+/- 4 weeks) for months 12-36, then every 12 months (+/- 6 weeks) until month 60.
- C. QOL Assessment at month 24 (+/- 4 weeks) (see section 8) or at time of post-treatment progression if applicable.
- D. Blood biology studies (see section 7) at 3-month post treatment and 12-month post treatment study visits, and at the time of post-treatment progression if applicable.
- E. See Section 7 for Optional Tumor Tissue and Concurrent Blood Sample.

6. DRUG INFORMATION

6.1. Poly-ICLC

Product: Polyinosinic-Polycytidylic acid – poly-L-lysine carboxymethylcellulose

Name: Poly-ICLC (Hiltonol®)

Poly-ICLC is classified as an investigational new drug. It is a synthetic complex of polyinosinic and polycytidylic acid, stabilized with polylysine and carboxymethyl cellulose. The thermal denaturation point is 89.5° C, about 40° C above that of plain polyI-polyC; the resistance to hydrolysis is several times that of the parent compound, and it induces peak levels of about 5000 IU of interferon per ml of serum in monkeys given 2 mg/kg intravenously.

The current study will be conducted under IND #43984, held by Oncovir. The drug to be used in this study is prepared and packaged in the GMP facility of Dalton Pharma Svcs, Toronto, ON, Canada, under the direction and under contract to Oncovir. It is then tested for identity (RNAase resistance and thermal denaturation) bioactivity, sterility and pyrogenicity before release for clinical experimental use.

FORMULATION: Supplied in 1 ml vials of 1.8 mg/ml opalescent solution/suspension = 1800 mcg/ml.

STORAGE: Should be refrigerated but NOT FROZEN. Stable at room temperature for 3 days.

SOLUTION PREPARATION: Solution is injected as supplied.

ADMINISTRATION: Administered as a single intramuscular injection twice per week.

Up to two doses can be obtained from the same vial. Instructions will be provided to patient/parents/guardian on how to draw, measure and administer the study medication.

SIDE EFFECTS: Discomfort at injection site, occasional malaise, myalgias, or fever. Rare transient leukopenia has been reported. At higher intravenous doses, transient liver enzyme and BUN elevations, and leukopenia have been reported. Idiosyncratic hypercoagulopathy has been reported in dogs at very high doses but has not been seen in humans. See investigator brochure.

MAXIMAL TOLERATED DOSE: As reported in cancer trials, 250-300 micrograms/kg.

